## **2. REGISTRATION PROCEDURES**

NA; Single Institution study.

## **3. OBJECTIVES**

OBJECTIVES	ENDPOINTS
Primary	

Phase 1b: To determine the safety and tolerability of neoadjuvant ascorbate in combination with preoperative EBRT as assessed by incidence of dose-limiting toxicities (DLT) in subjects with locally advanced high grade soft tissue sarcomas of extremity, trunk and retroperitoneum.
 
Phase 2: To estimate the efficacy of neoadjuvant ascorbate and radiotherapy as assessed by the pathological complete response rates (pCR) in subjects with locally advanced high grade soft tissue sarcomas. For this study, pCR will be defined as <math>\geq 95\%</math> tumor necrosis following concurrent radiation therapy and ascorbate.
	
Incidence of Dose Limiting Toxicities.
 
pCR rate- the proportion of subjects with pathologic tumor necrosis <math>\geq 95\%</math>.

Secondary	

Time to disease progression (local or distant recurrence)
 
Overall response rate (ORR) pre op as measured by RECIST 1.1 or a later tool for monitoring disease progression.
 
Overall survival rate (OS) at 2 Years
 
To grade radiation related skin toxicity overlying the tumor
	
Time from first day of study treatment to first documented disease progression.
 
The proportion of subjects with a complete or partial response.
 
Time from first day of study treatment to death due to any cause. Survival will be estimated at 2 years.
 
Incidence of radiation related skin toxicity by grade

OBJECTIVES	ENDPOINTS
To measure labile iron using T2* imaging sequence on MRI pre and post ascorbate treatments and compare with serum iron measurements	Changes in labile iron and serum iron from pre to post-treatments
To evaluate diffusion weighted imaging sequences on MRI in pre and post treatment tumors	Changes in diffusion weighted imaging sequence from pre-to post-treatment

### 3.1 Primary Objectives

**Phase 1b:** To determine the safety and tolerability of neoadjuvant ascorbate in combination with preoperative EBRT as assessed by incidence of dose-limiting toxicities (DLT) in subjects with locally advanced high grade soft tissue sarcomas of extremity, trunk and retroperitoneum.

**Phase 2:** To estimate the efficacy of neoadjuvant ascorbate and radiotherapy as assessed by the pathological complete response rates (pCR) in subjects with locally advanced high grade soft tissue sarcomas. For this study, pCR will be defined as  $\geq 95\%$  tumor necrosis following concurrent radiation therapy and ascorbate.

### 3.2 Secondary Objectives

- Time to disease progression (local or distant recurrence)
- Overall response rate (ORR) pre op as measured by RECIST 1.1 or a later tool for monitoring disease progression.
- Overall survival rate (OS) at 2 years
- To grade radiation related skin toxicity overlying the tumor as compared to historical controls
- To measure labile iron using T2\* imaging sequence on MRI pre and post ascorbate treatments and compare with serum iron measurements
- To evaluate diffusion weighted imaging sequences on MRI in pre and post treatment tumors and correlate it with necrosis and survival

## 4. PATIENT SELECTION

### 4.1 Inclusion Criteria

4.1.5 Subject or subject's legally acceptable representative has provided informed consent.

4.1.6 Histologically confirmed diagnosis of locally advanced soft tissue sarcoma of extremity, trunk or retroperitoneum that is unresectable with clear wide margins, for which preoperative radiotherapy is considered appropriate.

- Including metastatic (stage IV) disease for which radiotherapy and surgical resection of the primary tumor are indicated.

4.1.7 Patients with locally recurrent sarcoma after surgery alone are eligible for enrollment if

other inclusion criteria are met.

- 4.1.8 Patient does not have histologic subtypes: GIST, Desmoid, Ewing sarcoma, bone sarcomas and Kaposi sarcoma
- 4.1.9 Age  $\geq 18$  years.
- 4.1.10 Patients with history of non-melanomatous skin cancer, in situ carcinoma, or low-risk prostate cancer can be enrolled.
- 4.1.11 ECOG performance status  $\leq 1$ .
- 4.1.12 Tolerate one test dose (15g) of ascorbate.
- 4.1.13 Patient must have measurable disease:
  - Tumor size at least  $\geq 5$  cm in the longest diameter as measured by CT scan or MRI for which radiation is feasible and indicated.

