## 1. BACKGROUND

### 1.1 Disease Background

Adult soft tissue sarcomas (STS) constitute a wide heterogeneous group of very rare tumors, both in terms of histology and biological and clinical behavior. In contrast to major advances in the biological understanding of these heterogeneous subtypes, forward progress in the systemic treatment of sarcoma has been painstakingly slow. The prognosis of patients with metastatic or recurrent disease is poor and most of them will die from tumor progression. Taking into account differences in histology subtype, anatomic location of disease and age at disease onset, the overall median survival for patients with metastatic STS is approximately one year and only about 10% of these patients are alive at five years.

Control of localized disease is, therefore, of prime importance as evidenced by the National Comprehensive Cancer Network's (NCCN) current treatment guidelines. Pisters et al demonstrated that histologic grade, depth of location, and positive surgical margins are key determinants of STS recurrence. However, patients typically present late with local tumor extensions into critical adjacent structures, making complete surgical resection with uninvolved margins difficult. Preoperative radiotherapy has been shown to significantly improve local disease control, functional outcomes and survival in patients with locally advanced STS.

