## **11.2 Time to Disease progression (TTP)**

TTP is defined as the time from Enrollment until objective tumor progression including local and distant recurrences.

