**Response Measurement Criteria:**

Measurements of the tumor in its largest dimension should be obtained at baseline and at the end of the treatment phase, prior to surgical resection.

Response criteria should be by RECIST v 1.1.

- Complete response is the disappearance of all target lesions.
- Partial response is a 30% decrease in the sum of the longest dimensions of the target lesions, relative to baseline.
- Progressive disease is an increase of 20% or more in the sum of the longest dimension of target lesions
- Stable disease is a decrease in the tumor size of < 30% or an increase of < 20%.
- Antitumor response by pathologic assessment will be performed on the resected tumors. Pathologic assessment will be performed per institutional guidelines.
- The percent of tumor necrosis and the percent of tumor-infiltrating lymphocytes will be documented.
- Complete pathological response will be considered  $\geq 95\%$  pathologic tumor necrosis.

Radiologic response will be evaluated in this study using the new international criteria proposed by the revised Response Evaluation Criteria in Solid Tumors (RECIST) guideline (version 1.1) [*Eur J Ca* 45:228-247, 2009]. Changes in the largest diameter (unidimensional measurement) of the tumor lesions and the shortest diameter in the case of malignant lymph nodes are used in the RECIST criteria.

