### 12.2 Phase II

The primary objective of the Phase II portion of this study is to evaluate the proportion of patients with pathologic tumor necrosis  $\geq 95\%$ . Previous literature indicates approximately 10% of patients will achieve  $\geq 95\%$  tumor necrosis with pre-operative radiation therapy alone. A sample size of 25 patients achieves 81% power to detect a difference of 20% (from 10% to 30%) using a one-sided binomial exact test. The target significance level is 0.05 and the achieved level is 0.03. If 6 or more patients achieve  $\geq 95\%$  tumor necrosis, the treatment will be deemed worthy of further investigation. For secondary objectives, time to disease progression and overall survival will be estimated using the Kaplan-Meier method. Estimated survival probabilities will be plotted and medians reported, along with 95% confidence intervals. To identify differences in wound complication and Grade 3-4 dermatitis rates relative to historical controls, binomial point estimates and 95% exact confidence intervals will be reported. Mixed effects regression models will be used to estimate changes in labile iron and diffusion imaging sequences on MRI pre and post treatment.

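### TTP, pre-operative ORR and 2-year OS mix stage IV with non-metastatic patients, with no cap, no split by stage and no rule for metastases present at baseline

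*Combined protocol and SAP*

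**What the plan says.** Item 4.1.6 in Section 4.1 admits locally advanced soft tissue sarcoma and adds "Including metastatic (stage IV) disease for which radiotherapy and surgical resection of the primary tumor are indicated". No limit on the number of such patients is stated, and item 4.2.12 also allows treated brain metastases, so enrolling metastatic patients is deliberate. The objectives (Section 3) and the study design (Section 5.1) nevertheless describe a locally advanced, high-grade population.

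TTP appears in three forms:
- Objective (Section 3 table and Section 3.2): "Time to disease progression (local or distant recurrence").
- Endpoint column of the Section 3 table: "Time from first day of study treatment to first documented disease progression".
- Section 11.2: "TTP is defined as the time from Enrollment until objective tumor progression including local and distant recurrences".

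For pre-operative response, Section 11.3 says "Partial response is a 30% decrease in the sum of the longest dimensions of the target lesions, relative to baseline". It does not say which lesions may be targets. Section 12.2 says "time to disease progression and overall survival will be estimated using the Kaplan-Meier method", with medians and 95% confidence intervals. It plans no stratification, subgroup or separate analysis set by stage.

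Section 1.1 gives the outlook once disease is metastatic: "the overall median survival for patients with metastatic STS is approximately one year and only about 10" per cent alive at five years.

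**The concern.** A single-arm estimate of TTP or OS can only be read against outside experience, so it matters who is in the curve. A patient with stage IV disease still has distant disease after the primary is resected. Under the recurrence wording it is unclear what a distant event would be for that patient. Under the two progression wordings, growth of a metastasis that was there at entry and was never irradiated is an event. The same lesions can enter the sum of target lesions and so decide the pre-operative ORR.

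The plan neither limits nor predicts the stage IV share. Two versions of this trial with identical ascorbate effects could therefore report different TTP, ORR and 2-year OS purely through case mix, and the planned confidence intervals would not show it. The planned correlation of diffusion imaging with survival (Section 3.2) would carry the same confounding. The start of the TTP clock also differs: first study treatment in Section 3, enrolment in Section 11.2.

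**Working it through.** **The plan's own figure.** The documents state no figure for TTP, ORR or 2-year OS. The only calculation is the pCR rule in Section 12.2. For 6 or more of 25, the exact binomial gives one-sided alpha 0.0334 at a true rate of 10% (stated 0.03) and power 0.8065 at 30% (stated 81%). Both reproduce. This endpoint is necrosis in the resected tumour and does not use distant status.

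**Inputs.**
- Metastatic survival, from Section 1.1: median about 1 year, about 10% alive at 5 years.
- Number of patients: 25 at the recommended dose (Section 12.3), taken here as the set for OS.
- Non-metastatic 2-year OS, S_M0: not in the documents. Assumed 70–90%.
- Stage IV share, f: not in the documents. Shown for 10%, 20% and 30%.

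**Metastatic 2-year survival, S_IV.**
- Exponential through the median: 0.5² = 25%. This implies 0.5⁵ = 3% at 5 years, below the stated 10%.
- Weibull through both points: S(t) = exp(−ln 2 · t^k), with k = ln(ln 10 / ln 2) / ln 5 = 0.746. Then S(2) = exp(−0.693 × 2^0.746) = 31.3%.

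The range used is 25–31%.

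**Shift in pooled OS** = f × (S_M0 − S_IV). The smallest shift takes S_M0 = 70% and S_IV = 31.3%; the largest takes 90% and 25%. For f = 20%: 0.2 × (0.70 − 0.313) = 7.7 points, and 0.2 × (0.90 − 0.25) = 13.0 points.

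**Stage IV share of expected 2-year deaths** = f(1 − S_IV) / [f(1 − S_IV) + (1 − f)(1 − S_M0)]. With S_M0 = 80% and S_IV = 25%: 0.075/0.255 = 29% at f = 10%, 0.15/0.31 = 48% at 20%, and 0.225/0.365 = 62% at 30%.

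| Stage IV share | Shift, S_M0 70–90% | Pooled OS, S_M0 80% (S_IV 25% / 31.3%) | Share of deaths, S_M0 80% (S_IV 25% / 31.3%) |
|---|---|---|---|
| 10% | 3.9–6.5 points | 74.5% / 75.1% | 29% / 28% |
| 20% | 7.7–13.0 points | 69.0% / 70.3% | 48% / 46% |
| 30% | 11.6–19.5 points | 63.5% / 65.4% | 62% / 60% |

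**Against sampling error.** Exact 95% intervals at n = 25 are 54.9–90.6% for 19/25 and 42.5–82.0% for 16/25, a half-width of about 18 to 20 points. The shift at a 10% share is well inside that. At 20% it is still smaller than the half-width but no longer negligible. Unlike sampling error, it is systematic.

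**TTP and ORR.** The documents give no progression or response rates by stage, so no size can be put on either. The argument there rests on the definitions alone.

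**The case against.** A reader might infer that TTP is simply recurrence, so that the endpoints assume every patient is disease-free after surgery. The documents do not support that. The endpoint column in Section 3 and Section 11.2 both use progression. Section 11.2 includes recurrences without limiting events to them, and the clock starts with the tumour still in place. RECIST progression can be applied to a stage IV patient. This answers the strong reading but not the gap: three wordings coexist, and the broader two are the ones that mix growth of old metastases with recurrence after resection.

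A reader might also infer that TTP and OS mainly reflect how many metastatic patients enrol. The arithmetic does not bear that out. With 80% non-metastatic survival, stage IV patients supply under half of expected deaths at a 10% or 20% share and a majority only at 30%. No expected share is given. The Section 1.1 figures also describe metastatic sarcoma in general. Eligible patients have ECOG 0–1 and a primary judged suitable for radiotherapy and resection, so they may do better and the shift would shrink.

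It is also tempting to call distant progression irrelevant to a local treatment. Ascorbate is given intravenously and reaches high plasma levels, so distant outcomes are worth keeping.

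On ORR, Section 11.3 also speaks of measuring the tumour in the singular, and item 4.1.13 ties measurable disease to a lesion suitable for radiation. That suggests the primary is meant, but it leaves an ambiguity rather than a rule.

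Finally, these endpoints are secondary and descriptive, with no test or threshold, and stage is known, so a split could be made at reporting. That limits the weight of the point. A split chosen after the results are seen is weaker than one stated now.

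**Conclusion.** The point holds as a dependence on case mix that the plan does not control or report. TTP, pre-operative ORR and 2-year OS depend materially on the stage IV share and are hard to read for the locally advanced population in the objectives. They are not uninterpretable, and the documents do not show that case mix dominates them.

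For OS, a 20% stage IV share lowers the pooled 2-year estimate by about 8–13 points, and a 10% share by about 4–6.5. This rests on the Section 1.1 figures applying to the stage IV patients enrolled, which may be pessimistic, and on an assumed non-metastatic 2-year OS of 70–90%. TTP and ORR cannot be quantified. The primary pCR endpoint, the sample size and the 6-of-25 rule stand. This is a cheap improvement to secondary endpoints, not a flaw in the trial's main decision.

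**What to change.** - Sections 3, 3.2 and 11.2: use one TTP definition and one start date throughout.
- Section 11.2: for patients metastatic at baseline, state that progression is RECIST progression from baseline, and report its local and distant components separately.
- Section 12.2: report TTP and 2-year OS by baseline M status, with M0 patients as the main estimate and the stage IV and pooled results alongside.
- Section 11.3: state that ORR is measured on the irradiated primary, with whole-body RECIST response as supportive.
- Keep stage IV patients in the pCR analysis, which concerns the resected primary only.

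The cost is wording. Baseline stage is already available from the screening imaging in Section 10.2, and eligibility, sample size and the pCR rule do not change. The M0 intervals will be somewhat wider: with 5 stage IV patients of 25, the M0 set is 20, and at the same event proportion the interval grows by a factor of about √(25/20) = 1.12.

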## 4.2 Exclusion Criteria

4.2.1 Inadequate organ function within 21 days of Day 1 of study as defined by:

- Hemoglobin < 9.0 g/dL
- Absolute neutrophil count (ANC) </= 1500 per mm^3
- Platelet count </= 100,000 per mm^3
- Total bilirubin >/= 1.5 × ULN. Subjects with direct bilirubin < ULN with total bilirubin levels > 1.5 X ULN will not be excluded.
- Aspartate aminotransferase (AST) or alanine aminotransferase (ALT) > 2.5 × ULN
- Alkaline phosphatase > 2.5 × ULN
- PT (or INR) and PTT (or aPTT) >/= 1.5 × ULN
- Creatinine > 2.0 × ULN

4.2.2 G6PD (glucose-6-phosphate dehydrogenase) deficiency

4.2.3 Prior history of two episodes of symptomatic oxalate kidney stones within last year.

4.2.4 Prior radiation therapy in excess of 20 Gy to the site of the current diagnosis of sarcoma. No overlap with prior radiation fields in excess of 20 Gy is allowed.

4.2.5 Prior history of receiving pharmacological ascorbate.

4.2.6 Patients actively receiving insulin therapy AND needing daily fingerstick for glucose monitoring.

4.2.7 Concurrent, clinically significant, active malignancies within two years of study enrollment.

4.2.8 Female subjects who are pregnant or breast-feeding, or planning to become pregnant during study treatment and through 3 months after the last dose of study treatment.

4.2.9 Female subjects of childbearing potential or male subjects who are unwilling to use 2 highly effective methods of contraception during study treatment and through 3 months after the last dose of study treatment.

4.2.10 Currently receiving treatment in another invasive investigational device or drug study, or less than 30 days since ending treatment on another investigational device or drug study(s).

4.2.11 Patients who are on the following drugs and cannot have a drug substitution: flecainide, methadone, amphetamines, quinidine, and chlorpropamide. High dose ascorbic acid may affect urine acidification and, as a result, may affect clearance rates of these drugs.

4.2.12 Known CNS disease, except for treated brain metastasis: Treated brain metastases are defined as having no evidence of progression or hemorrhage after treatment and no ongoing requirement for dexamethasone, as ascertained by clinical examination and brain imaging (MRI or CT) during the screening period. Anticonvulsants (stable dose) are allowed. Treatment for brain metastases may include whole brain radiotherapy (WBRT), radiosurgery (RS; Gamma Knife, LINAC, or equivalent) or a combination as deemed appropriate by the treating physician. Patients with CNS metastases treated by neurosurgical resection or brain biopsy performed within 3 months prior to Day 1 will be excluded

4.2.13 History of allergic reactions attributed to compounds of similar chemical or biologic composition to ascorbate

- 4.2.14 Uncontrolled intercurrent illness including, but not limited to, ongoing or active infection, symptomatic congestive heart failure, unstable angina pectoris, cardiac arrhythmia, or psychiatric illness/social situations that would limit compliance with study requirements.
- 4.2.15 Known HIV-positive and hepatitis B & C individuals. High-dose ascorbate acid is a known CYP450 3A4 inducer, which results in lower serum levels of antiretroviral drugs
- 4.2.16 Patients who are on warfarin and cannot have a drug substitution or who decline the drug substitution.

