## 5.4 Study Timeline Schema:

## Phase 1b schema:

## Phase 2 schema:

## 5.5 Post-consent Screening Procedures

If subjects fail the G6PD or test doses of ascorbate, they are considered a screen failure.

- G6PD test (off-site test, so draw immediately). If subject has a prior G6PD test, this can be used as G6PD levels do not fluctuate (i.e., there is no window for this test).
- One test dose of 15g of ascorbate. A physician must review the patient's medication list against the list of medications prohibited on this trial prior to the test dose of ascorbate.

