### 8.2 Compatibility

Ascorbate is considered a CYP4503A4 inhibitor. Therefore close monitoring of subjects who may be concomitantly receiving CYP3A4 substrates with narrow therapeutic indexes for toxicities is required. A table of CYP3A4 substrates, inhibitors, and inducers is provided in the Appendix. Ascorbate may decrease plasma/blood concentrations of substrates (Appendix B, tables 1, 2, and 3). Ascorbate may increase CYP3A4 induction (Appendix B, Table 4).

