## PROTOCOL APPENDIX B: CYP3A4 INTERACTION TABLE

### CYP3A4 INTERACTION TABLE

(Ascorbate may decrease the plasma/blood concentrations of substrates)

Drugs with ~~strikeout~~ text are antiretroviral drugs that are not allowed for use on this study.

\* 3A4 substrate & inhibitor; # 3A4 substrate & inducer

abiraterone	acetaminophen	ado-trastuzumab	alfentanil
alfuzosin	aliskiren	alitretinoin	almotriptan
alprazolam	ambrisentan	amiodarone*	amitriptyline
amlodipine	amprenavir	apixaban	aprepitant*
aripiprazole	armodafinil#	artemether	asenapine
astemizole	atazanavir*	atorvastatin	avanafil
axitinib	beclomethasone	bedaquiline	benzphetamine
bexarotene	bisoprolol	boceprevir	bortezomib
bosentan#	bosutinib	brentuximab	bromazepam
bromocriptine	budesonide	buprenorphine	buspirone
busulfan	cabazitaxel	cabozantinib	caffeine
canagliflozin	carbamazepine#	cevimeline	chlor diazepoxide
chloroquine	chlorpheniramine	ciclesonide	cilostazol
cinacalcet	cisapride	citalopram	clarithromycin*
clindamycin	clobazam	clomipramine	clonazepam
clopidogrel	clorazepate	clozapine	cobicistat*
cocaine	codeine	colchicine	conivaptan*
crizotinib	cyclobenzaprine	cyclophosphamide	cyclosporine*
dantrolene	dapsone	darifenacin	<del>darunavir</del>
dasatinib	delavirdine*	desogestrel	dantrolene
dexamethasone#	dexlansoprazole	dextromethorphan	diazepam
diclofenac	dienogest	dihydroergotamine	diltiazem*
disopyramide	docetaxel	dofetilide	dolasetron
domperidone	donepezil	doxorubicin	dronedarone
droperidol	dutasteride	efavirenz*#	eletriptan
elvitegravir	enzalutamide	eplerenone	ergoloids
ergonovine	ergotamine	erlotinib	erythromycin*
escitalopram	esomeprazole	estazolam	estradiol
estradiol valerate	estrogens	eszopiclone	ethinyl estradiol
ethosuximide	etonogestrel	etoposide	etravirine
everolimus	exemestane	felbamate	felodipine
fentanyl	fesoterodine	fexofenadine	finasteride
fingolimod	flunisolide	flurazepam	flutamide
fluticasone	<del>fosamprenavir</del> *	fosaprepitant	fulvestrant
galantamine	gefitinib	gransetron	guanfacine
haloperidol*	hydrocodone	hydrocortisone	ifosfamide
iloperidone	imatinib*	imipramine	indacaterol
<del>indinavir</del> *	irinotecan	isosorbide dinitrate	isosorbide mononitrate

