### CYP3A4 INTERACTION TABLE

(Ascorbate may decrease the plasma/blood concentrations of substrates)

Drugs with ~~strikeout~~ text are antiretroviral drugs that are not allowed for use on this study.

\* 3A4 substrate & inhibitor; # 3A4 substrate & inducer

isradipine	itraconazole*	ivacaftor	ixabepilone
ketamine	ketoconazole*	lansoprazole	lapatinib
lercanidipine	letrozole	levonorgestrel	lidocaine*
linagliptin	lomitapide	loperamide	<del>lopinavir</del>
loratadine	losartan	lovastatin	lumefantrine
lurasidone	<del>maraviroc</del>	marijuana	medroxyprogesterone
mefloquine	meloxicam	mestranol	methadone
methylergonovine	methylprednisolone	miconazole*	midazolam
mifepristone	mirabegron	mirtazapine	modafinil
mometasone	montelukast	nateglinide	nefazodone*
<del>nelfinavir*</del>	<del>nevirapine#</del>	nicardipine*	nifedipine
nilotinib	nimodipine	nisoldipine	nitrendipine
norethindrone	norgestrel	nortriptyline	omeprazole
ondansetron	ospemifene	oxybutynin	oxycodone
paclitaxel	paliperidone	palonosetron	pantoprazole
paricalcitol	paroxetine	pazopanib	perampanel
perphenazine	pimozide	pioglitazone	pomalidomide
ponatinib	prasugrel	prednisolone	prednisone
primaquine	progesterone/ progestins	propafenone	propranolol
quazepam	quetiapine	quinidine*	quinine
rabeprazole	ramelteon	ranolazine	regorafenib
repaglinide	rifabutin#	<del>rilpivirine</del>	risperidone
<del>ritonavir*</del>	rivaroxaban	roflumilast	romidepsin
ruxolitinib	salmeterol	<del>saquinavir*</del>	saxagliptin
selegiline	sertraline	sibutramine	sildenafil
silodosin	simvastatin	sirolimus	sitagliptin
solifenacin	sorafenib	sufentanil	sunitinib
tacrolimus	tadalafil	tamoxifen	tamsulosin
<del>telaprevir</del>	telithromycin*	temsirolimus	teniposide
terfenadine	testosterone	tetracycline*	theophylline
tiagabine	ticagrelor	ticlopidine	tinidazole
<del>tipranavir</del>	tofacitinib	tolterodine	tolvaptan
topotecan	toremifene	tramadol	trazodone
triazolam	trimethoprim	trimetrexate	trimipramine
ulipristal	vandetanib	vardenafil	vemurafenib
venlafaxine	verapamil*	vilazodone	vinblastine
vincristine	vinorelbine	vismodegib	voriconazole
warfarin	zaleplon	zileuton	ziprasidone
zolpidem	zonisamide	zopiclone	

References:

1. Lexi-comp On-line. Cytochrome P450 Enzymes: Substrates, Inhibitors, and Inducers. (accessed 1/16/15)
2. Pharmacist's Letter/Prescriber's Letter. Cytochrome P450 Drug Interactions. October 2013.

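### The contraception rule (4.2.9, 5.9) does not limit method type, so two hormonal methods would satisfy it, although Appendix B says ascorbate may lower contraceptive hormones

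*Combined protocol and SAP*

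**What the plan says.** Section 4.2.9 of the protocol excludes "Female subjects of childbearing potential or male subjects who are unwilling to use 2 highly effective methods of contraception during study treatment" and for 3 months afterwards. Section 5.9 lists a woman's failure to use two such methods among the grounds on which ascorbate may be stopped. Neither section defines the term, lists acceptable methods or asks for a non-hormonal one.

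Appendix B is a table of CYP3A4 substrates under the statement that "Ascorbate may decrease the plasma/blood concentrations of substrates". Its entries include "ethinyl estradiol" and "levonorgestrel". The only entries it bars are the struck-out "antiretroviral drugs that are not allowed for use on this study".

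Two provisions act on concomitant drugs in general. Section 5.5 requires, before the test dose: "A physician must review the patient's medication list against the list of medications prohibited on this trial". Section 8.2 says that "close monitoring of subjects who may be concomitantly receiving CYP3A4 substrates with narrow therapeutic indexes for toxicities is required". Section 8.2 also opens with "Ascorbate is considered a CYP4503A4 inhibitor", then goes on to say that substrate levels may fall and that induction may increase.

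For two other kinds of drug the plan does respond to a possible loss of effect. Section 4.2.15 calls ascorbate a CYP3A4 inducer and gives lowered antiretroviral levels as the reason for an exclusion. Section 5.8.1 advises caution with ondansetron because it may work less well alongside ascorbate.

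**The concern.** Two methods are required so that one still protects if the other fails. If both are hormonal and both hormones are substrates whose levels the study drug may lower, one cause could weaken both, and the redundancy is less than it appears. The protocol flags the interaction in its own appendix but does not carry it into its own contraception rule.

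What is at stake is patient and fetal safety during an investigational infusion given with radiation, in a trial that excludes pregnancy (4.2.8). The estimate of pathological response, the sample size and the decision rule are not involved.

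**Working it through.** No stated figure bears on this point, so the check sets the provisions side by side.

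1. **What satisfies the rule.** Sections 4.2.9 and 5.9 set a number (2) and a quality (highly effective), but no type. Two hormonal methods therefore meet the wording. This follows from silence, not from an explicit permission.

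2. **What the interaction table covers.** The first part of Appendix B lists desogestrel, ethinyl estradiol and etonogestrel, among others. The second part lists levonorgestrel, medroxyprogesterone and norethindrone, among others. That makes 3 + 3 = 6 examples, not a complete count. Reading them as contraceptive hormones is this review's classification; the appendix does not group drugs by use.

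3. **Whether an existing check catches the combination.**
   - The medication review in 5.5 is against prohibited drugs. In the supplied text, the drugs that are barred or must be substituted are those in 4.2.11, warfarin (4.2.16) and the struck-out antiretrovirals. None is a hormonal contraceptive.
   - The monitoring in 8.2 covers toxicity of narrow-index substrates. A lowered contraceptive level is a loss of effect, which it does not address.
   - Concomitant medications are recorded (5.8) and reviewed during treatment (10.1), so a hormonal product would be seen. No instruction says what to do about it.
   - The calendar in 10.1 marks a pregnancy test at screening only, and 10.2 places it within 7 days of week 1 day 1. Note b defers to institutional guidelines, which are not supplied.
   - Pregnancy is a ground for stopping ascorbate in 5.9, but that acts after the event.

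4. **Direction of the interaction.** Four statements point to lower substrate levels: 4.2.15 (inducer), the Appendix B header, and two later sentences of 8.2. One points the other way: the opening sentence of 8.2 (inhibitor). The opening sentence is the outlier.

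5. **Period of dosing.** The 15 g test dose comes in the week before radiation (5.6.3). After that, 15 doses (5.3) at 3 per week take 15 / 3 = 5 weeks, which agrees with 25 fractions at 5 per week: 25 / 5 = 5.0 weeks. For 28 fractions at the same assumed rate, radiation lasts 28 / 5 = 5.6 weeks. Sections 5.2 and 5.6.5 end ascorbate with radiation.

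The gap is therefore one unconnected pair of provisions, for one subgroup, over roughly 5 to 6 weeks of dosing plus the test dose.

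**The case against.** The strongest reply is that a method weakened by the study drug is arguably no longer highly effective, so an investigator could reject it under the existing words. That reading is reasonable, but it relies on each investigator linking 4.2.9 to Appendix B unprompted. The documents do not ask for that.

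It can also be said that the interaction is unsettled. Appendix B is a general substrate list under a single cautious statement, no size is given for any hormone, and 8.2 contradicts itself on direction. This stands as a limit on how strongly the point can be put. It does not remove it, because the plan already acts on the same kind of interaction for antiretrovirals and cautions about it for ondansetron.

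Finally, the consent pages were removed and the supplied appendices go from B to D, so contraceptive advice may exist elsewhere. That stands too, and the point is confined to the supplied text.

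A reader might infer three stronger things that the documents do not support:

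- **That hormonal contraception will fail on ascorbate.** The appendix says only that levels may decrease. It gives no magnitude and no clinical consequence.
- **That the period at risk includes the 3 months after the last dose.** Those months are how long contraception is required. Nothing says the interaction lasts that long.
- **That dose holds or toxicity delays lengthen exposure.** Ascorbate stops when radiation ends, and no text says that a hold extends treatment.

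**Conclusion.** The point holds as a minor one. The wording of 4.2.9 and 5.9 lets both required methods share an interaction that the protocol itself flags, and the supplied text contains no contraceptive caution.

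It affects only women of childbearing potential relying on two hormonal methods. A woman with one non-hormonal method keeps that protection. The affected group is probably small, and the documents give no count. The conclusion assumes that the named Appendix B entries are used as contraceptives, that the direction of effect is the one stated in Appendix B and 4.2.15, and that the removed or unsupplied pages do not already deal with the matter. No statistical result of the trial changes.

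Section 5.9 asks men for a single method, where 4.2.9 asks for two. This is a drafting mismatch of little consequence, because 4.2.9 already sets two methods during treatment and for 3 months after.

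**What to change.** In 4.2.9 and in the female criterion of 5.9, add: *for women of childbearing potential, at least one of the two methods must be non-hormonal*. State the test by method type alone. Tying it to the Appendix B list as well would create a second, different test, since a hormone absent from the list would pass one and fail the other.

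In 8.2, replace inhibitor with inducer, so that the section agrees with 4.2.15, Appendix B and its own later sentences; the sponsor can confirm this against the source cited there. In the same section, extend the monitoring to loss of effect of the listed substrates.

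As a drafting correction only, align the male criterion in 5.9 with the two methods in 4.2.9.

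The cost is a few words in three sections, with matching consent wording if it is not already there. The practical downside is that a few women must add or change a method before entry. No endpoint, sample size or analysis is touched.
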